1 INVESTIGATIONAL TEAM

Refer to the trial specific contact list for details of investigators, sponsor personnel, clinical research organization personnel and facilities used in the study.

2 INTRODUCTION: BACKGROUND AND SCIENTIFIC RATIONALE

2.1 Mild Traumatic Brain Injury

Concussion or mild traumatic brain injury (mTBI) is defined as a blow or jolt to the head (i.e., a non-penetrating head injury) that disrupts the normal function of the brain. Concussion can be described as a brain injury defined by a complex pathophysiological process that is induced by biomechanical forces. Mild traumatic brain injury is described as a continuum of brain injury and associated pathophysiology of mild vs. more severe trauma-induced brain injury.¹ Recent years has seen greater emphasis placed on the importance of brainstem systems impaired as a result of diffuse axonal injury resulting from inertial forces imparted by mTBI damaging axonal pathways traversing the interface of the cerebral hemispheres and the brainstem.²⁻⁴ Autonomic function which controls eye movement, balance and neck control appears to be vulnerable to concussive injury. Injury to this pathway may result in impairments in a number of daily functions such as reading or driving⁵ which may predispose concussed individuals for more prolonged deficits, and the need for earlier, symptom-targeted therapies.

Traumatic brain injury (TBI) is a major cause of death and disability in all age groups and is responsible for significant healthcare costs. Concussion management consensus statements consistently call for the need for additional research to improve outcomes for this patient population.^{6,7}

Accurately identifying the true incidence and duration of ongoing symptoms following concussion has remained elusive, with no reliable way to confirm that symptomatic recovery coincides with brain physiologic recovery.⁹ The diagnosis of concussion relies on self-reported symptoms, which are prone to both over-reporting (e.g., in anxious individuals and malingerers⁵); and under-reporting (e.g., in both athletes and members of the military⁸). An estimated 20% of individuals have persistent post-concussive symptoms (PPCS), as defined by symptoms lasting 2 or more weeks in adults, and 4 or more weeks in adolescents.¹⁰ The 2 best validated instruments for assessing symptom persistence are the Post-Concussion Symptom Inventory (validated in youth from age 5 to 18 years of age¹¹) and the Post-Concussion Symptom Scale (PCSS) (validated in adults¹² and in 13 to 22 year olds¹³). Four distinct symptom clusters: cognitive-fatigue-migraine, affective, somatic, and sleep have been identified as being affected following a concussion.¹³ The presence of pre-existing neuropsychological conditions, especially anxiety, as well as a lack of resilience, have been implicated as contributing to PPCS. Other factors contributing to the severity and duration of post-concussive symptoms have been identified including sex, age, extent of athleticism, history of prior concussions, as well as a history of migraine headaches. Consistent with the objectives of this clinical trial, symptoms of autonomic dysfunction, including exercise-induced headaches, are amongst most prevalent during the first week post-injury, and have also been reported to be the most persistent following mTBI.⁵

Autonomic dysfunction in the form of impaired cerebral autoregulation is commonly seen following mTBI.¹⁵ Standard clinical evaluations are able to assess the integrity of eye movement, balance, and neck function¹⁴, however, there is no easy way to assess autonomic

function in clinical settings. Options for diagnosing autonomic dysfunction following concussion include the Buffalo Concussion Treadmill Test (BCTT);¹⁶ a test performed within a week of injury that has the ability to predict prolonged recovery in concussed adolescents with a sensitivity of 73% and a specificity of 78%.¹⁷ and the “ice bucket test” (also known as the cold pressor test);¹⁸ a simpler and faster way to diagnose autonomic dysfunction following mTBI¹⁹.

[figure not shown]
The current standard of care for patients with mTBI is cognitive and physical rest. However, a recently conducted randomized control trial suggests that the implementation of exercise activity as opposed to physical and cognitive rest during the initial period of injury accelerates recovery.²⁰ Sub-symptom threshold aerobic exercise, has been shown to improve autonomic function as reflected by non-invasive measures such as heart rate variability (HRV),²¹ and to accelerate recovery following concussion.

It is anticipated that results from our study, in combination with those evolving from similar research studies now underway in Australia as well as the US, will provide support for decision making by physicians, trainers, and other clinicians during the days/weeks following concussion, including what activities should be avoided, what therapies can accelerate recovery, and when the brain has recovered so that it is safe to resume sport or work.

2.2 Therapeutic Intervention

A number of governing bodies now endorse an active rehabilitation program of progressive reintroduction of noncontact aerobic activity that does not exacerbate symptoms along with close monitoring of symptom expression.²²

In order to promote this, ANSwers Neuroscience Pty Ltd has developed a novel therapeutic intervention, downloadable to an Apple i-touch or i-phone device, that provides a telemetry-based graded exercise program which enables remote monitoring of symptoms. The sponsor will provide an i-touch or i-phone to each eligible subject during the Baseline Visit, which they will use daily during the 8 weeks of clinical study. Subjects keep the i-touch or i-phone on completion of study participation. The digital therapeutic application permits the ‘dosing of heart rate (HR)’ approach²³ while monitoring symptomatic and physiologic recovery on a daily basis. It is hypothesized that the mobile application, ClearPlay©, will accelerate recovery time following concussion by improving activity-induced blood flow to the brain and aid in the rehabilitation process. ClearPlay© is intended to be used in a professional setting following point of injury or onset of the condition and can also be used by patients at home. Refer to Figure 1 for an image of the ClearPlay© interface.

Figure 1: Sample of ClearPlay© Interface

To support the use of ClearPlay©, ANSwers Neuroscience Pty Ltd has developed 2 devices:

- ClearHeart©, a Cooling Glove System as an alternative to ice bucket testing, to enable providers to perform a quick, real-time diagnosis of autonomic nervous system disorders, including mTBI. The results are available immediately through a computer interface, permitting healthcare providers to make immediate diagnostic assessments and therapeutic recommendations.
- ClearNeck© a prototype device for cervico-genic proprioception measurement. This test is based on the joint position error test to assess “whiplash”.

2.3 Clinical Studies

Historically, concussion has been described as a cognitive injury and patients have been advised not to engage in any cognitive or physical exertion while symptomatic. More recently, however, concussion has been described as a physiological injury affecting both the heart and autonomic nervous system, and patients suffering from prolonged concussion-related symptoms and deficits have been encouraged to begin aerobic exercise as part of their concussion care. While intensive exercise too soon after concussion has been associated with delayed recovery and used to justify prolonged periods of rest, recent studies have shown that controlled, sub-symptom threshold aerobic exercise may aid recovery by improving autonomic balance and cerebral blood flow auto-regulation after concussion.

2.4 Known and Potential Risks

Potential risks exist to the following groups of patients:

- Subjects with musculoskeletal or cardiac or pulmonary conditions that preclude participation in exercise;
- Subjects using anti-hypertensive medications;
- Subjects with peripheral circulatory disorders due to conditions such as, but not limited to, Raynaud's syndrome, scleroderma, or diabetes. These subjects may experience hand discomfort when exposed to the ClearHeart© cooling;
- Subjects with lymphedema in the left arm, as they may experience arm discomfort when using the ClearHeart© device.

2.6 Risk Assessment

As this is a therapeutic intervention study, there are minimal risks associated with taking part in this investigational study. The current standard of care for subjects with mTBI is cognitive and physical rest. However, a number of governing bodies now endorse an active rehabilitation program following concussion and clinical trials have also been completed to assess the safety of graded exercise following mTBI.

During the study, appropriately trained staff will ensure that any risks associated with the study, including exercise testing, are closely monitored. Real time review of safety data will

be performed, with safety monitoring to be adjusted as required if any risks become apparent. Enrolment of subjects will only occur at study sites that have appropriately trained staff to ensure subjects receive the best standard of care.

3 STUDY OBJECTIVES

3.1 Primary Objective

The primary objective of the study is to compare the effects of graded exercise and passive stretching using ClearPlay© (ANSwers Neuroscience Pty Ltd commercial mobile application) on recovery following mTBI in the Australian setting.

3.2 Secondary Objectives

The secondary objectives of the study are to:

- Compare the safety and tolerability of graded exercise compared to passive stretching following mTBI;
- Develop a composite physiologic scale to predict the magnitude and duration of ongoing post-concussive symptoms;
- Validate the performance of ClearHeart©, ANSwers Neuroscience Pty Ltd commercial prototype for cold pressure testing, compared to ice bucket testing.

3.3 Exploratory Objectives

The exploratory objectives of the study are to:

- Validate the performance of ClearNeck©, ANSwers Neuroscience Pty Ltd commercial prototype based on the joint position error test to assess “whiplash”.

4 STUDY DESIGN AND ENDPOINTS

4.1 Description of the Study Design

This study is designed as an open label study of a therapeutic intervention in subjects who have sustained mTBI. At least 400 subjects aged 14 to 45 inclusive will be enrolled in this study at up to 5 study sites. Subjects will be randomly assigned with a ratio of 1:1 to complete either graded exercise or passive stretching. The study sites will have well-established concussion research programs and referral populations.

The therapeutic intervention is either 20 minutes daily of graded exercise or 20 minutes daily of passive stretching delivered through the ClearPlay© mobile application, downloaded to an Apple i-touch or i-phone device, used in conjunction with a wrist-worn heart rate monitoring device (Waveband®). The sponsor will provide one i-touch or i-phone to each subject to provide them with access to ClearPlay App. This device will also allow subjects to access music for use during exercise or stretching.

Randomization of each subject will occur when the subject has completed all of their Baseline physiologic testing (Ice Bucket Test, ClearHeart© and BCBT) on Day 0.

[figure not shown]
Both the site staff treating subjects and the subjects themselves will be aware of the assigned exercise regimen. Subjects will be stratified based on baseline scores on the PCSS (threshold ≥ 30).

The study consists of 2 study visits and 3 remote telephone visits between the 2 study visits:

- Study Visit 1 (Day 0) – Screening/Baseline visit: within 3 to 14 days of concussion. This visit will serve as a screening visit, to determine eligibility to participate in the study. Eligible subjects will be enrolled, and baseline assessments performed;
- Remote telephone safety assessments – Day 14, Day 28 and Day 42 for safety follow up;
- Study Visit 2 – Follow-up visit: 8 weeks following enrolment (Day 56).

A schematic diagram of the study design is presented in Figure 2.

Figure 2: Study Design

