4.2 Study Objectives and Endpoints

The study objectives and endpoints to be evaluated in this study are presented in Table 1.

Table 1: Study Objectives and Endpoints

Objectives	Endpoints
Primary Objectives	Primary Endpoints
To compare the effects of graded exercise to passive stretching using ClearPlay© on symptomatic recovery rate following mTBI.	
 • Within-subject analysis of change in symptoms over time using the PCSS, comparing short-term ‘survival rates’ between graded exercise and stretching using Kaplan-Meier analyses for days since concussion.
Secondary Objectives	Secondary Endpoints
To compare the safety and tolerability of graded exercise to passive stretching in patients following mTBI.	
 • Adverse events reported from Day 1 through Day 56, including those identified during exercise or passive stretching during the 20 minutes of daily therapy.
To compare symptom resolution following graded exercise compared to passive stretching using ClearPlay© following mTBI.	
 • Within subject analysis of change in the number of subjects who are symptom free at 8 weeks between the 2 groups. Symptom free is defined by subjects having 3 consecutive days of PCSS scores lower than pre-concussion. 
Note: This objective is similar to the primary one, with the primary endpoint being recovery (binary outcome) vs. symptom resolution (continuous variable).
 
 • Determine differences in symptomatic recovery based on gender, baseline scores on the PCSS, baseline athletic fitness (Godin leisure-time exercise questionnaire), the history of injury, a history of migraine, as well as the presence of pre-morbid anxiety.
To compare the effects of graded exercise to passive stretching using ClearPlay© on physiologic recovery rate following mTBI.	
 • Within subject analysis of normalization of physiologic measurements obtained during the BCBT comparing data collected on entry to the study on Day 0 vs. follow up on Day 56 including: 
 - Beat to beat BP; • Determine differences in physiologic recovery based on gender, baseline scores on the PCSS, baseline athletic fitness (Godin leisure-time exercise questionnaire), the history of injury, a history of migraine, as well as the presence of pre-morbid anxiety (BAI; BSI-18; ASI).

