5 STUDY ENROLMENT AND WITHDRAWAL

5.1 Inclusion Criteria

To be eligible for study entry subjects must satisfy all of the following criteria:

1. Male or female subjects aged ≥ 14 to ≤ 45 , able and willing to provide informed consent (≥ 18 years), or informed consent is obtained by the parent or legal guardian for minor subjects, with the minor providing age appropriate assent, according to local law and regulations;

2. Subject is fluent in English, able to understand and agree to comply with protocol requirements, and complete all assessments;
3. Subject has a history of recent concussion as diagnosed by a health care professional within 3 to 14 days of enrolment;

Note: Concussion is defined as a head injury/blow to the head resulting in any of the following 3 signs and/or new symptoms: (1) amnesia for less than 24 hours; (2) Loss of consciousness for less than 30 minutes; (3) Glasgow Coma Scale score ≥ 13 ; (4) Dazed and Confused/bell rung; with at least 1 new symptom or augmentation of a previous symptom on the PCSS as compared with baseline at the time of enrolment, including: headaches, dizziness, fatigue, irritability, insomnia, difficulty concentrating, and/or memory difficulties; (5) The composite symptom score on the PCSS must be at least 3 points higher post-concussion than pre-concussion.

4. Subject has daily access to the internet.

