6.3.2 Randomization

A computer-generated randomization schedule will be prepared by a statistician prior to the start of the study. Treatment allocation will be made per the randomization list.

After signing the informed consent form/providing assent, subjects will be administered the screening instruments via REDCap Cloud, along with generation of unique subject ID.

Once eligibility has been established, subjects must proceed to complete all Baseline assessments. The Order of Assessment is listed in Section 8.1, Table 4. Randomization of each subject will occur when the subject has completed all of their Baseline physiologic testing on Day 0.

The subject will be assigned a unique randomization number, which will be allocated sequentially based on the pre-determined randomization schedule, and according to their chronological order of inclusion in the study.

Both the unique subject ID and randomization numbers will be used to identify the subject throughout the study period and on all study-related documentation.

Stratification: randomization will be stratified at each enrolment site by the baseline symptom severity score on the PCSS (threshold $<$ or ≥ 30). The baseline PCSS score is reflective of multiple pre-morbid, neurologic, psychologic, and other factors that collectively are likely to significantly impact the presence of PCSS. Rather than stratify the population based on

individual factors, the single composite measure should provide the most efficient and effective starting point for this clinical trial.

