9.6 Efficacy Analysis

The full presentation of the analysis of efficacy data will be presented in the SAP.

For all subjects, daily reported PCSS scores collected from ClearPlay© mobile application will be utilized to determine the resolution of symptoms. The resolution of symptoms is defined as a symptom-severity score of less than each subject's pre-injury PCSS score for 3 consecutive days. To assess differences in the probability of symptom resolution between graded exercise and passive stretching during the 8 weeks of therapy, both unadjusted and adjusted logistic regression models will be used. The primary outcome of the study will be to confirm or refute the superiority of sub-threshold aerobic exercise versus passive stretching to result in resolution of symptoms following mTBI. Confounders for the adjusted models will include age, gender, anxiety at baseline, history of migraine, cardiovascular fitness, the presence or absence of neurologic findings, and site of enrollment.

The survival probability will be compared using Kaplan-Meier (log rank test) analyses between the 2 treatment arms. Cox proportional hazards regression models will be used to evaluate the differences in time to symptom resolution. Adjusted treatment effects will be estimated in Cox proportional hazards regression models, controlling for the variables listed above. To identify that our randomization strategy was effective, analysis of variance will be used to assess for group-wise differences in age, days since injury to initial visit, initial PCSS score, resting HR, and Δ HR during the BCBT and resting BP and Δ BP during the ice bucket test on Day 1. Non-parametric tests of medians will be used to compare the non-normally distributed variable duration of clinical recovery. Chi-squared tests will be used to assess group-wise differences in gender, history of concussions, and incidence of PPCS.

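### The adjusted logistic and Cox models contain no PCSS term, although randomization is stratified on PCSS and resolution is judged against each subject's own pre-injury PCSS

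*Protocol*

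**What the plan says.** **Randomization.** Section 4.1: "Subjects will be stratified based on baseline scores on the PCSS". Section 6.3.2 says that "randomization will be stratified at each enrolment site by the baseline symptom severity score on the PCSS", with two levels, below 30 and 30 or more. Sections 4.1 and 4.3 use the same cut. The reason given is prognostic: "The baseline PCSS score is reflective of multiple pre-morbid, neurologic, psychologic, and other factors".

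**Endpoint.** Section 9.6: "The resolution of symptoms is defined as a symptom-severity score of less than each subject's pre-injury PCSS score for 3 consecutive days". Table 1 in 4.2 agrees: "Symptom free is defined by subjects having 3 consecutive days of PCSS scores lower than pre-concussion".

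**Adjusted models.** Section 9.6, repeated in the synopsis: "Confounders for the adjusted models will include age, gender, anxiety at baseline, history of migraine, cardiovascular fitness". Presence of neurologic findings and site of enrolment complete the list. The adjusted Cox models use the same variables.

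**Where PCSS appears otherwise.** The difference between post- and pre-injury scores is used only for eligibility (5.1): "The composite symptom score on the PCSS must be at least 3 points higher post-concussion than pre-concussion". The absolute baseline score appears in a secondary analysis of differences in recovery (Table 1), and the initial score in the balance check (9.6). Table 5 shows that pre- and post-injury PCSS are both collected at the Day 0 visit.

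**The concern.** Two things do not fit together.

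First, the trial randomizes within PCSS strata because it regards the score as prognostic, but then leaves every form of that score out of the models that estimate adjusted treatment effects. Site, the other stratification factor, is kept.

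Second, the endpoint is relative and the stratum is absolute. A subject who scores 28 before and 31 after injury is eligible, belongs to the upper stratum and is 3 points above the pre-injury level. A subject who scores 2 before and 29 after belongs to the lower stratum and is 27 points above it. The stratum ranks these two in the opposite order from the distance that the endpoint asks them to cover.

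At stake are some precision in the adjusted estimates and the ability to correct a chance imbalance in starting distance. The validity of the randomized test is not at stake.

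**Working it through.** **1. The plan's own figure.** Inputs from 9.1: 80% and 93% resolution, α = 0.05, power 90%. Two-sided, pooled variance, mean rate 0.865:

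n = [1.960·√(2·0.865·0.135) + 1.282·√(0.80·0.20 + 0.93·0.07)]² / 0.13² = (0.947 + 0.608)² / 0.0169 ≈ 143.1, so 144 per arm (288 in total).

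With the continuity correction, n′ = (n/4)·[1 + √(1 + 4/(n·0.13))]² ≈ 158.1 per arm. This is 316 in total if rounded to the nearest integer and 318 if rounded up, so the stated 316 reproduces. With 400 randomized and 15% attrition, 400 × 0.85 = 340 are evaluable (170 per arm). Uncorrected power is then 0.94.

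**2. How much of the distance the stratum captures.** The protocol gives no PCSS distribution, so these are assumptions: pre-injury score gamma with mean/SD 5/6, 10/10 or 15/12; excess = 3 + gamma (mean 18, SD 14), hence mean 21. Share of the variance of log excess explained:

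| Predictor | Mean pre-injury 5 | 10 | 15 |
|---|---|---|---|
| Stratum at 30 | 48% | 40% | 34% |
| Post-injury score | 72% | 56% | 49% |
| Post- and pre-injury scores, linear | 85% | 85% | 85% |

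The last row falls short of 100% only because of the log scale; the raw excess is exactly post minus pre. Up to 26% of the upper stratum has a below-median distance.

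**3. Logistic power, 340 evaluable.** Simulation with 1,500 runs (Monte Carlo SE about 1 point at power near 75%) and an assumed log-odds of 0.7 or 1.2 per SD of log excess:

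| Model | 80% vs 90% (0.7 / 1.2) | 80% vs 93% (0.7 / 1.2) |
|---|---|---|
| Unadjusted | 0.730 / 0.735 | 0.952 / 0.963 |
| Stratum | 0.747 / 0.756 | – |
| Post-injury score | 0.752 / 0.771 | – |
| Excess | 0.763 / 0.791 | 0.956 / 0.974 |

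At 80% vs 90% the excess gains 3.3 and 5.6 points over no adjustment. The post-injury score alone gains 2.2 and 3.6 points, about two-thirds of that (2.2/3.3 = 0.67; 3.6/5.6 = 0.64). At 80% vs 93% the gain is 0.4 and 1.1 points.

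A second simulation (1,000 runs, 80% vs 93%) assumed slopes of 0.5 to 1.5 per SD of distance and a correlation of 0.5 or 0.9 between the distance and the score behind the stratum. Power was 0.94–0.96 unadjusted, 0.94–0.96 with the stratum and 0.95–0.98 with stratum plus distance. Adding the distance to the stratum model therefore gains about 0 to 2 points. Type I error was 0.034–0.047, 0.036–0.052 and 0.041–0.061 respectively (SE about 0.007), so omission does not inflate it.

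**4. Cox model.** Exponential times, pre-injury mean 10, 340 evaluable, 600 runs (SE up to 2 points), assumed log-hazard slope of 0.3 to 0.7 per SD of log excess. At 80% vs 93%, power is at least 99% in every model. At 80% vs 90%, the excess gains 5 to 7 points over no adjustment. The hazard ratio also depends on what is conditioned on: at 80% vs 93% the log hazard ratio is 0.53 unadjusted and 0.62 adjusted for slope 0.5, and 0.55 and 0.70 for slope 0.7.

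**The case against.** **The distance is not shown to be the main prognostic factor.** A reader might infer that the trial leaves out its most important predictor. The documents do not support this: no section ranks the distance above baseline PCSS or the other listed factors, and the simulations assume its strength. This objection stands. What can be said is that the distance is built into the endpoint and is therefore likely to be strongly prognostic.

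**The result might be thought biased.** It is not. Allocation is randomized, and the simulated type I error stays near 5%. The lower unadjusted hazard ratio reflects non-collapsibility: it is a different quantity, not a biased comparison.

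**The gain is negligible at the planned effect.** This stands for power: 0 to 2 points. The larger gains need an effect smaller than the protocol assumes.

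**Severity is already partly handled.** This also stands. The absolute score is balanced by stratification, checked at baseline and examined in Table 1. A reader might infer that adding the post-injury score would be useless because equal scores can lie at different distances. The figures contradict that: it recovers about two-thirds of the simulated gain.

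**A single excess term would be a poor fix.** This stands and shapes the fix. Under the strict rule in 9.6, and assuming a scale minimum of 0, a subject with a pre-injury score of 0 cannot resolve whatever the excess. The level of the threshold matters as well as the distance. (Section 6.1 words its three-day rule with equality allowed; the two sections must be reconciled separately.)

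**It is SAP detail, and the log-rank comparison is untouched.** The second half is right: the Kaplan-Meier and log-rank analyses do not change. The first half is weaker. Section 9.6 names a covariate list, and 9.2 says the SAP follows the protocol's principal features. The wording does not bar further terms, so the correction is easy.

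**Conclusion.** The point holds as a modest improvement to a stated model. The adjusted logistic and Cox models omit a stratification factor while keeping the other one, and omit both scores that fix where each subject starts and must finish.

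The cost is precision and uncorrected chance imbalance: about 0 to 2 points of logistic power at 80% versus 93%, and about 3 to 6 points over no adjustment at 80% versus 90%, with Cox figures of similar size at 80% versus 90% (5 to 7 points). These sizes rest on assumed PCSS distributions and prognostic slopes, since the protocol gives neither. The textual finding that no PCSS term is listed rests on no assumption.

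**What to change.** Keep the stratified randomization as it is.

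In 9.6 and the synopsis, add to the covariates of the adjusted logistic and Cox models:
- the PCSS randomization stratum (below 30, or 30 and above);
- the Day 0 post-injury PCSS and the pre-injury PCSS, both continuous. Entering the excess plus the pre-injury score is equivalent. Either form covers both the distance and the level of the threshold.

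In Table 1, examine symptomatic recovery by the excess (Day 0 post-injury minus pre-injury) as well as by absolute baseline PCSS.

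Cost: no new data and no change in procedure, as both scores are collected on Day 0. There are two small downsides. The pre-injury score is recalled after injury and carries some error. The logistic model also gains up to three terms while non-resolvers are few: at the planned rates, 170 × 0.20 + 170 × 0.07 ≈ 46 among 340. With treatment, six single-term covariates and up to four site indicators (11 terms), that is about 4.2 non-resolvers per term, falling to about 3.3 with 14. The SAP should say how sparse sites are handled. The Cox model has about 340 − 46 = 294 events and is not strained.
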